10. TREATMENT OF PATIENTS

10.1. Selection and Timing of Dose for Each Patient

Once a patient is enrolled, the appropriate dose of ACE-536 will be administered as a subcutaneous injection on Cycle 1 Day 1. Subsequent doses will be administered every 3 weeks on Day 1 of the cycle. Study day 85 (\pm 2 days) is the last possible study day that ACE-536 can be administered, regardless of the cycle. Dose reductions may be required for individual patients as outlined in the Patient Dose Modifications Rules ([Section 10.8.1](#)). If a dose delay is required, the patient will return weekly for assessment of hematology results and adverse events until the patient is eligible to receive the next dose of ACE-536. Patients will be asked to return to the clinic for two follow-up visits, occurring approximately 28 days and 56 days after their last dose of ACE-536. If a patient has a positive anti-drug antibody (ADA) result at the last visit, the patient may be asked to return for additional ADA testing every three months, until a negative result is obtained or the result is considered to be stabilized.

10.2. Concomitant Medications

During screening and throughout the study patients may take stable doses of medications for chronic conditions that are not specifically excluded by the protocol (see [Section 9.3.1](#) and [Section 9.3.2](#)). If a patient requires treatment with any new medications that are specifically excluded by the eligibility criteria, the patient will be discontinued from the study and should complete the end of treatment visit and enter the follow-up period of the study. The investigator should consult the medical monitor regarding any questions about whether a new medication or dosage of existing medication would require the patient to discontinue from the study. Concomitant medications will be collected beginning at study screening and will include all medications taken within 28 days prior to Cycle 1 Day 1.

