9.4. Patient Treatment Discontinuation and Withdrawal Criteria

Patients will be informed that they have the right to withdraw from the study at any time for any reason without prejudice to their medical care.

A patient may be discontinued from treatment for any of the following reasons:

- Patient's request
- Patient's unwillingness or inability to comply with the protocol
- Pregnancy
- Use of prohibited medication (e.g., hydroxyurea)
- Medical reason or adverse event, at the discretion of the investigator and/or the medical monitor
- Hypersensitivity reaction to study drug
- At the discretion of the sponsor (e.g., termination of the study or a dose level)

A patient may be withdrawn from the study for any of the following reasons:

- Patient's request
- Patient's unwillingness or inability to comply with the protocol
- Death
- Loss to follow-up
- At the discretion of the sponsor (e.g., termination of the study)

The reasons for study withdrawal and treatment discontinuation must be recorded in the patient's CRF. The investigator must notify the sponsor, the medical monitor and the contract research organization (CRO) immediately when a patient has been discontinued/withdrawn due to an AE. Patients who discontinue treatment early should complete the end of treatment (EOT) follow-up visit at the time of discontinuation and then complete the end of study (EOS) follow-up visit approximately 28 days later.

The investigator must notify the sponsor and the CRO when a patient has been discontinued/withdrawn for reasons unrelated to the study or study drug (e.g., withdrawn consent, lost to follow up).

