10.2.1. Other Treatments for β -Thalassemia

If treatment with hydroxyurea is required during the ACE-536 treatment period, the patient should be discontinued from treatment with study drug and complete the end of treatment visit and enter the follow-up period. Iron chelation therapy is allowed if initiated at least 56 days prior to C1D1.

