5.7. Efficacy Analyses

All efficacy endpoint will be performed using the ITT population.

All efficacy summaries will be presented by dose cohort and for NTD and TD patients separately. In addition, the dose cohorts will be combined and presented as low dose group and high dose group. Low dose group includes patients on 0.2 and 0.4 mg/kg dose cohorts. High dose group includes patients on 0.6 mg/kg and above. No formal hypothesis testing is planned.

In general, below rules apply to the derivations of efficacy endpoints which utilize hemoglobin and RBC transfusion data unless specified otherwise:

- Hemoglobin measurements within 14 days following RBC transfusion will be excluded from efficacy analysis
- For each patient, all efficacy endpoints will be derived based on an analysis cut-off day, defined as the last dose + 56 days or the last date from transfusion record data, whichever is earlier.

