5.7.1. Primary Efficacy Endpoint

The primary efficacy endpoint is the proportion of β -thalassemia patients who have an erythroid response, defined as below:

- For non-transfusion dependent (NTD) patients, a hemoglobin increase of ≥ 1.5 g/dL from baseline sustained for ≥ 14 days (in the absence of RBC transfusions). Hemoglobin measurements within 14 days following RBC transfusion or after 56 days of last dose will be excluded from analysis.
- For transfusion dependent (TD) patients, a $\geq 20\%$ reduction in RBC transfusion burden during any rolling 12-week window on treatment compared to baseline. The rolling 12-week window starts on Day 1 and increments by 1 day, e.g., from day 1 to day 84, day 2 to day 85, day 3 to day 86, etc. The search window ends on last dose day + 56 days or last day of hemoglobin measurement, whichever is earlier.

A point estimate of the proportion of patients having a response will be presented along with its associated exact 95% confidence interval based on binomial distribution for NTD and TD patients separately.

The complete hemoglobin measurements and RBC transfusion records will be listed for each patient.

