5.11. Protocol Deviations

Protocol deviations will be listed for the following categories:

- Not meeting inclusion/Exclusion criteria
- Withdraw criteria met, but subject not discontinued: we not have any patients who fall in this category; will be noted as such in CSR
- Failure to perform key procedures
- Study treatment deviation
- Prohibited concomitant medication
- GCP related deviation

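### Protocol 9.4, 10.2 and 10.2.1 disagree on what follows hydroxyurea use, and the SAP has no data cut when an excluded drug starts, so later data can count toward the primary response

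*Protocol*

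**What the plan says.** **Protocol.** Section 9.4 gives use of a prohibited medication, with hydroxyurea as the example, in a list headed "A patient may be discontinued from treatment for any of the following reasons". It is absent from the separate list of reasons for withdrawal from the study. SAP 3.2 repeats both lists. Section 10.2, on any new medication that the eligibility criteria exclude, says "the patient will be discontinued from the study and should complete the end of treatment visit and enter the follow-up period of the study". Section 10.2.1 opens with "If treatment with hydroxyurea is required during the ACE-536 treatment period" and continues "the patient should be discontinued from treatment with study drug and complete the end of treatment visit and enter the follow-up period".

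**SAP.** All efficacy analyses use all enrolled patients (4.1, 5.7). Section 5.7 sets a cut-off day for every efficacy endpoint, "defined as the last dose + 56 days or the last date from transfusion record data, whichever is earlier". For the primary endpoint in non-transfusion-dependent (NTD) patients, 5.7.1 adds: "Hemoglobin measurements within 14 days following RBC transfusion or after 56 days of last dose will be excluded from analysis". For TD patients, 5.7.1 searches every rolling 12-week window from Day 1 until 56 days after the last dose, or the last hemoglobin if that is earlier. An excluded drug started on study is named only in 5.11, where "Prohibited concomitant medication" is a category of protocol deviation to be listed. The table of changes in 5.13 does not mention it.

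**The concern.** The trial has no control arm, and a patient is a responder if any qualifying stretch of data is found. The SAP already removes hemoglobin values that a transfusion may have raised. It has no matching rule for another treatment of the disease, although Protocol 10.2.1 itself places hydroxyurea under other treatments for β-thalassemia. A hemoglobin rise or a fall in transfusions that occurs on the other drug could therefore be scored as an ACE-536 response, and no comparator would reveal it.

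The protocol inconsistency adds to this. A site that reads 10.2 as ending study participation produces no later data. A site that keeps the patient in follow-up produces data that the SAP then counts. The endpoint would depend partly on which sentence the site followed.

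**Working it through.** **1. The protocol provisions side by side, for hydroxyurea.**
- 9.4: may; leaves treatment; no period stated.
- 10.2: will; leaves the study, yet the same sentence sends the patient to follow-up of the study.
- 10.2.1: should; leaves treatment; only if needed during the ACE-536 treatment period.

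Both the force and the object differ. For any other excluded drug, 10.2.1 drops out and two provisions remain.

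**2. The plan's own figure.** The only design figure is about 87% power for n = 30, 30% against 10%, one-sided 0.05 (Protocol 15.3). The normal approximation with continuity correction 1/(2n) gives z = (0.30 − 0.10 − 1/60 − 1.645 × √(0.09/30)) / √(0.21/30) = 1.11, a power of 86.75%. It reproduces and is not in dispute.

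**3. Drug started after the Day 85 dose.** Counting ends on Day 85 + 56 = Day 141.
- NTD: the scheduled hemoglobins still to come are Days 92, 99, 113 and 141. With a start on Day 86 all four are on the other drug. They span 141 − 92 = 49 days, and the response needs 14.
- TD: the last 84-day window runs from Day 58 to Day 141. A start on Day 86 puts 141 − 86 + 1 = 56 days on the other drug, and 56/84 = 67%.
- Stopping study drug has no further effect by then, and 10.2.1 does not clearly apply. Only 10.2 speaks to the case, and it is ambiguous on whether the patient stays.

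**4. Early discontinuer who starts the drug at the end-of-treatment (EOT) visit.** EOT takes place at discontinuation and the end-of-study (EOS) visit 28 ± 7 days later, so the gap is 21 to 35 days.
- NTD: EOS is the only scheduled hemoglobin after the start. A rise sustained from EOT to EOS needs the EOT value to be at least 1.5 g/dL above baseline already, before the other drug could act. The route needs unscheduled hemoglobins, or a start before EOT.
- TD: the search stops at the last hemoglobin, so the overlap is about 21 to 35 of 84 days (25% to 42%).
- A full window requires last dose day + 56 ≥ 84, that is, a last dose on Day 28 or later. With one or two on-schedule doses (Days 1 and 22) the search ends on Day 57 or Day 78, and no TD response can be scored. With a last dose on Day 43 it ends at the latest on Day 99, which leaves 99 − 83 = 16 windows. If EOT is Day 64 and EOS Day 92, 92 − 83 = 9 remain.

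**5. Fall in transfusions that the other drug would have to produce.** Assume a constant pretreatment rate and no ACE-536 effect. A 20% fall over 84 days that is achieved entirely within d days needs a fall of 0.20 × 84/d in that stretch: 30% for d = 56, 48% for d = 35, 60% for d = 28, 80% for d = 21. In whole units, for an assumed 8 units per 12 weeks, response needs 2 fewer (2/8 = 25%):
- d = 56: 2/5.33 = 37.5%
- d = 35: 2/3.33 = 60%
- d = 28: 2/2.67 = 75%

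A partial ACE-536 effect would lower these figures.

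**6. Weight of one patient.** SAP 5.7.1 estimates the rate for NTD and TD separately. In an expansion stratum at its minimum of 12, one patient is 1/12 = 8.3 points. If the other stratum holds the remaining 18, one patient there is 1/18 = 5.6 points.

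**The case against.** The case on the other side is substantial.

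- **The sections agree in practice.** 10.2 and 10.2.1 both lead to an EOT visit and then follow-up, and 9.4 can be read as a general list of permitted reasons rather than a rule. This narrows the gap but does not close it: one sentence still ends study participation and another only treatment.
- **SAP 5.11 reports no patient who met withdrawal criteria and was not discontinued.** This weakens any worry about patients left on ACE-536 with the other drug. It does not cover those who stopped, or had finished dosing, and were then followed.
- **The SAP is descriptive and lists medications, hemoglobin and transfusions by patient.** A confounded responder could be found in the listings, but would still be in the reported rate. Counting all ITT data is a legitimate choice if it is stated as one; here it arises by omission.

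Three stronger inferences are not supported. A reader might infer that any early discontinuer could be scored a responder because of the other drug. Step 4 shows that the NTD route largely fails on scheduled visits and that some TD patients have no full window. A reader might take 67% overlap as typical, but on the visit schedule it is essentially reachable only after the Day 85 dose. A reader might also infer that the reported rate is in fact inflated. The documents do not say how many patients started such a drug, how large or fast its effect is, or why hydroxyurea was excluded, and not every excluded drug need raise hemoglobin.

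**Conclusion.** The point holds in a limited form. The protocol is inconsistent on hydroxyurea, less so on other excluded drugs, and the SAP's counting rules do not remove data obtained after such a drug starts. The bias is possible, not shown, and would act toward a higher response rate. Exposure is greatest after the Day 85 dose and smaller for early discontinuers.

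The conclusion rests on two assumptions: that some patients start an excluded therapy that affects hemoglobin within 56 days of their last dose, and that they remain under observation. The number is probably small, but a stratum may have as few as 12 patients. This is a cheap improvement worth making, not a flaw that overturns the design.

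**What to change.** Add one rule to SAP 5.7, before database lock. Exclude hemoglobin and transfusion data from the first dose of hydroxyurea, or of another excluded therapy expected to affect hemoglobin, with those therapies named in advance. Require the NTD response, or the TD 12-week window, to be complete before that date; otherwise score the patient as a non-responder in ITT. Report the all-data ITT result as a sensitivity analysis, and state whether the partial-date imputation in 5.12.2 applies to the start date.

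Protocol 9.4, 10.2 and 10.2.1, with SAP 3.2, must be reconciled so that one statement says whether the patient leaves treatment or the study, and over what period. Which clinical rule is right is not judged here.

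The cost is one SAP rule, one extra summary and some protocol wording. Medication dates are already collected and used (SAP 5.6.1), so no new data are needed. The response rate may be slightly lower, because a response to ACE-536 that was completed only after the other drug began would no longer count. If nobody was affected, the result does not change.

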10.2.1. Other Treatments for β -Thalassemia

If treatment with hydroxyurea is required during the ACE-536 treatment period, the patient should be discontinued from treatment with study drug and complete the end of treatment visit and enter the follow-up period. Iron chelation therapy is allowed if initiated at least 56 days prior to C1D1.

10.2.2. RBC Transfusions

Concurrent treatment for anemia with blood transfusions is allowed at the discretion of the investigator, for low hemoglobin levels, symptoms associated with anemia (e.g., hemodynamic or pulmonary compromise requiring treatment) or a comorbidity.

For any RBC transfusions received during the study, collect hemoglobin values just prior to transfusion.

Each TD patient in the expansion cohort will have a defined “pre-transfusion hemoglobin threshold” which will be calculated based on transfusion history and will be used for determining when to transfuse during the study. The baseline pre-transfusion hemoglobin threshold will be the mean of all documented pre-transfusion hemoglobin values during the 12 weeks prior to

C1D1. During treatment, if the pre-transfusion hemoglobin value is increased by ≥ 1 g/dL compared to the baseline pre-transfusion hemoglobin threshold for that patient, transfusion should be delayed by a minimum of 7 days and/or the number of units transfused should be reduced by 1 or more RBC units. Patients may be transfused at the investigator's discretion for symptoms related to anemia or other requirements (e.g., infection).

For the first dose of ACE-536, dosing should occur after a minimum of 7 days post-transfusion; subsequent doses should not be given within 24 hours of transfusion or planned transfusion.

10.3. Treatment Compliance

ACE-536 will be administered as a SC injection at the clinical site by the study staff and will be documented in the study record. Monitoring for patient compliance with the treatment regimen is therefore unnecessary.

10.4. Randomization

This is an open-label study that does not require randomization.

10.5. Treatments Administered

Patients will continue to receive the same dose level of study drug as they were assigned at study entry unless a dose modification is required (see [Section 10.8](#)).

10.6. Dose-Limiting Toxicity Definition

A Dose-Limiting Toxicity (DLT), using the current active minor version of the National Cancer Institute Common Toxicity Criteria for Adverse Events version 4.0 (NCI-CTCAE v4.0), is defined as any of the following toxicities, at any dose level occurring within 28 days of the first administered dose:

- Treatment related serious adverse event (SAE) of Grade ≥ 3
- Treatment related non-hematologic adverse event (AE) of Grade ≥ 3
- Treatment related hematologic AE of Grade ≥ 4 .

10.7. Safety Evaluation and Dose Escalation

Safety will be evaluated by the Safety Review Team (SRT), which is comprised at minimum of the coordinating investigator, medical monitor, and an independent hematologist. The role of the SRT will be described in greater detail in the SRT Charter. The SRT will review safety data when a minimum of 3 patients in a cohort have completed Study Day 29, including dose-limiting toxicities (DLTs), adverse events (AEs), serious adverse events (SAEs), laboratory results (including hematology and chemistry), vital signs, and erythroid response data. The SRT may make one or more of the following recommendations to the sponsor:

- Enroll 3-6 patients in an additional cohort at a higher or lower dose level, not to exceed modified Fibonacci dose escalation scheme (see [Section 9.1](#)); enrollment in current cohort may be closed after a minimum of 3 patients.

- Proceed to the expansion cohort, with a recommended starting dose level for TD and NTD patients, not to exceed the maximum dose level evaluated in the dose escalation cohorts.
- Postpone a decision pending collection of additional data from the current cohort.
- Recommend that no further cohorts should be enrolled in the study.

SRT recommendations to escalate or reduce the dose level of ACE-536 in a subsequent cohort, or complete enrollment of 6 patients in the current cohort, will be based in part upon the following criteria:

- If a DLT occurs in ≤ 1 patient in a cohort within 28 days following the initial dose of ACE-536, dose escalation may occur;
- If a DLT occurs in ≥ 2 patients in a cohort within 28 days of the initial dose, the dose level for the next cohort (if any) should not be escalated; a lower dose may be recommended.
- If a hemoglobin increase of ≥ 2.0 g/dL (confirmed within 48 to 72 hours and not attributable to RBC transfusion) occurs in ≥ 2 patients in a cohort within 28 days of the initial dose, the dose level for the next cohort (if any) should not be escalated; a lower dose may be recommended.

10.8. Patient Dose Modification and Titration

Patients in the dose escalation cohorts have a pre-determined dose level based on cohort number (see [Section 9.1](#)). Dose level titration is not allowed for patients in the dose escalation cohorts, but dose delay or reduction may be required according to Patient Dose Modification Rules ([Section 10.8.1](#)). Examples of dose level reductions for patients in dose escalation cohorts are included in [Table 2](#) below. Patients who require more than 2 dose reductions due to an AE should be discontinued from treatment and complete the end of treatment and end of study visits.

All patients in the expansion cohort will be initially treated with ACE-536 at an assigned starting dose level (to be determined) which has been deemed to be safe, well tolerated, and at least minimally effective by the SRT. Examples of possible expansion cohort starting dose levels and associated modifications (reductions and titrations) are in [Table 2](#). Rules for individual patient titrations are described in [Section 10.8.2](#) for NTD patients and [Section 10.8.3](#) for TD patients.

Table 2: Starting Dose Levels, Dose Level Reductions (All Cohorts), and Dose Level Titrations (Expansion Cohort Only)

2 nd Dose Reduction	1 st Dose Reduction	Starting Dose Level	1 st Dose Titration	2 nd Dose Titration
0.2 mg/kg	0.4 mg/kg	0.6 mg/kg	0.8 mg/kg	1.0 mg/kg
0.4 mg/kg	0.6 mg/kg	0.8 mg/kg	1.0 mg/kg	1.25 mg/kg
0.6 mg/kg	0.8 mg/kg	1.0 mg/kg	1.25 mg/kg	1.5 mg/kg
0.8 mg/kg	1.0 mg/kg	1.25 mg/kg	1.5 mg/kg	N/A
1.0 mg/kg	1.25 mg/kg	1.5 mg/kg	N/A	N/A

- Dose titration to higher dose levels is only applicable to patients in the expansion cohort.
- Expansion cohort starting dose level for TD and NTD patients to be determined by the sponsor in conjunction with the SRT (range: 0.2-1.5 mg/kg).
- Dose titration will not exceed the maximum dose level tested in the dose escalation cohorts and determined to be safe and well tolerated by the SRT.
- Patients may increase and decrease dose level per protocol as needed, however patients who require more than 2 dose reductions due to an AE should be discontinued from treatment and complete the end of treatment and end of study visits.

10.8.1. Patient Dose Modification Rules

The following dose modification rules include both pharmacodynamic and safety parameters which may require a dose delay and possibly a dose reduction. These rules should be assessed prior to dosing. If a dose delay is required the patient should have weekly visits to assess hematology results and adverse events until the patient is eligible to receive the next dose of ACE-536.

Observation on Dosing Day	Action	ACE-536 Dose Modification ^a
Hemoglobin \geq 13 g/dL	Hold dose and monitor patient weekly until hemoglobin $<$ 12 g/dL	Resume dosing once hemoglobin $<$ 12 g/dL.
Hemoglobin increase \geq 2 g/dL from the previous dosing day (not attributable to RBC transfusion)	Continue dosing	Reduce dose by 1 dose level ^b
Non-hematologic adverse event \geq Grade 3, or hematologic adverse event \geq Grade 4, at least possibly related to study drug	Hold dose and monitor patient weekly until resolution of AE to \leq Grade 1 or baseline	Resume dosing upon resolution of the AE to \leq Grade 1 or baseline and reduce dose level by 1 dose level ^b

^a Last possible treatment day is Study Day 85 (\pm 2 days).

^b All subsequent doses will remain at the new dose level or can be reduced further if needed. Patients who require more than 2 dose reductions due to an AE should be discontinued from treatment and complete the end of treatment and end of study visits.

